### **Control of calluses**

Before initiating treatment with regorafenib:

- Check condition of hands and feet.
- Suggest a manicure/pedicure, when indicated.
- Recommend pumice stone use for callus or ‘rough spot’ removal.

During regorafenib treatment:

- Avoid pressure points.
- Avoid items that rub, pinch or create friction.

### **Use of creams**

- Non-urea based creams may be applied liberally.
- Keratolytic creams (e.g. urea-based creams, salicylic acid 6%) may be used sparingly and only to affected (hyperkeratotic) areas.
- Alpha hydroxyl acids (AHA) based creams may be applied liberally 2 times a day. Approximately 5% to 8% provides gentle chemical exfoliation.
- Topical analgesics (e.g. lidocaine 2%) are to be considered for pain control.
- Topical corticosteroids like clobetasol 0.05% should be considered for subjects with Grade 2 or 3 HFSR. Avoid systemic steroids.

### **Tender areas should be protected as follows:**

- Use socks/gloves to cover moisturizing creams
- Wear well-padded footwear
- Use insole cushions or inserts (e.g. silicon, gel)
- Foot soaks with tepid water and Epson salts

#### **7.2.4. Grading and Dose Adjustments for Hypertension**

Hypertension is a known AE associated with regorafenib treatment. Subject will have their blood pressure measured at least weekly at the study site during the first 6 weeks of treatment. If additional blood pressure measurements are done outside the study site, and the blood pressure is > 140 mm Hg systolic or > 90 mm Hg diastolic (NCI CTCAE v4.0), then the subject must contact study personnel. The management of hypertension, including the choice of antihypertensive medication, will be performed according to local standards and to the usual practice of the Investigator. Every effort should be made to control blood pressure by medical means other than study drug dose modification. If necessary, Table 7.4 outlines suggested dose reductions.

**Table 7.4: Management of Treatment-Emergent Hypertension**

Grade (CTCAE v4.0)	Antihypertensive Therapy	Regorafenib Dosing
1  Prehypertension (systolic BP 120 - 139 mmHg or diastolic BP 80 - 89 mmHg)	None	
 
Continue regorafenib
 
Consider increasing blood pressure (BP) monitoring
 

2  Systolic BP 140 - 159 mmHg or diastolic BP 90 - 99 mmHg, OR Symptomatic increase by > 20 mmHg (diastolic) if previously within normal limits	
 
Treat with the aim to achieve diastolic BP < 90 mm Hg:
 
If BP previously within normal limits, start anti-hypertensive monotherapy
 
If subject already on anti-hypertensive medication, titrate up the dose.
 
	
 
Continue regorafenib
 
If symptomatic, hold regorafenib until symptoms resolve AND diastolic BP ≤ 90 mm Hga. When regorafenib is restarted, continue at the same dose level.
 

3  Systolic BP ≥ 160 mmHg or diastolic BP ≥ 100 mmHg OR More than one drug or more intensive therapy than previously used indicated	
Treat with the aim to achieve diastolic BP ≤ 90 mm Hg: Start anti-hypertensive medication
 
AND/OR Increase current anti-hypertensive medication
 
AND/OR Add additional anti-hypertensive medications.
	
 
Hold regorafenib until diastolic BP ≤ 90 mm Hg, and if symptomatic, until symptoms resolve.a
 
When regorafenib is restarted, continue at the same dose level.
 
If BP is not controlled with the addition of new or more intensive therapy, reduce by 1 dose level.b
 
If Grade 3 hypertension recurs despite dose reduction and antihypertensive therapy, reduce another dose level.c
 

4  Life-threatening consequences (eg, malignant hypertension, transient or permanent neurologic deficit, hypertensive crisis)	Per institutional guidelines	Discontinue therapy

a. Subjects requiring a delay of >4 weeks should go off protocol therapy

b. If BP remains controlled for at least one cycle, dose re-escalation permitted per Investigator's discretion.

c. Subjects requiring $\geq 2$ dose reductions should go off protocol therapy.
--

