### 7.2.2. Dose Adjustments for Adverse Events (other than hand-foot-skin reaction, hypertension and liver function test abnormalities)

The following tables outline dose adjustments for toxicities related to study drug except hand-foot skin reaction, hypertension and liver function test abnormalities.

**Table 7.1: Recommended dose modification for toxicities except hand-foot-skin reaction, hypertension and ALT/AST/Total Bilirubin**

NCI-CTCAE v4.0 a	Dose Interruption	Dose Modification b	Dose for Subsequent Cycles
Grade 0-1	Treat on time	No change	Dose escalation or No change (see section 6.1.1.2)
Grade 2	Treat on time	No change	No change
Grade 3	Delay until $\leq$ Grade 2 c	Reduce by 1 dose level	If toxicity remains $<$ Grade 2, dose re-escalation can be considered at the discretion of the treating Investigator. If dose is re-escalated and toxicity ( $\geq$ Grade 3) recurs, institute permanent dose reduction.
Grade 4	Delay until $\leq$ Grade 2 c	Reduce by 1 dose level.  Permanent discontinuation can be considered at treating Investigator's discretion.	

a. NCI-CTCAE = National Cancer Institute - Common Terminology Criteria for Adverse Events, version 4.0  
 b. Excludes alopecia, non-refractory nausea/vomiting, non-refractory hypersensitivity and nonclinical and asymptomatic laboratory abnormalities.  
 c. If no recovery after a 4 week delay\*, treatment should be permanently discontinued

The table above outlines dose adjustments for hematologic and non-hematologic toxicities related to regorafenib except HFSR and hypertension. In addition to these recommended dose modifications, subjects who develop diarrhea, mucositis, anorexia or other events predisposing to fluid loss or inadequate fluid intake should be carefully monitored and rehydrated as clinically necessary. This is in order to minimize the risk of postural hypotension and renal failure.

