**Table 7.3 Recommended dose modification for hand-foot-skin reactiona**

Grade of event (NCI-CTCAE v4.0)	Occurrence	Suggested Dose Modification
Grade 1	Any	Maintain dose level and immediately institute supportive measures for symptomatic relief
Grade 2	1 st occurrence	Consider decreasing dose by one dose level and immediately institute supportive measures. If no improvement, interrupt therapy for a minimum of 7 days, until toxicity resolves to Grade 0-1 b, c
	No improvement within 7 days or 2 nd occurrence	Interrupt therapy until toxicity resolves to Grade 0-1. c When resuming treatment, treat at reduced dose level b
	3 rd occurrence	Interrupt therapy until toxicity resolves to Grade 0-1. c When resuming treatment, decrease dose by one dose level. b, d
	4 th occurrence	Discontinue therapy
Grade 3	1 st occurrence	Institute supportive measures immediately. Interrupt therapy for a minimum of 7 days until toxicity resolves to Grade 0-1. c When resuming treatment, decrease dose by one dose level. b, d
	2 nd occurrence	Institute supportive measures immediately. Interrupt therapy for a minimum of 7 days until toxicity resolves to Grade 0-1. c When resuming treatment, decrease dose by one additional dose level b, d
	3 rd occurrence	Discontinue treatment permanently.

a. More conservative management is allowed if judged medically appropriate by the Investigator.  
b. If toxicity returns to Grade 0-1 after dose reduction, dose re-escalation is permitted at the discretion of the Investigator if subject has completed one cycle at reduced dose without recurrence of event.  
c. If there is no recovery after a 4-week delay, treatment with regorafenib will be discontinued permanently.  
d. Subjects requiring > 2 dose reductions should go off protocol therapy.  
e. The maximum daily dose is 160 mg.

At first occurrence of HFSR, independent of grade, prompt institution of supportive measures such as topical emollients, low potency steroids, or urea-containing creams should be administered.

Recommended prevention/management strategies for skin toxicities consistent with HFSR are summarized below:

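### Table 7.4: the Grade 3 hypertension hold can be triggered by systolic pressure alone but is released on diastolic pressure alone

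*Combined protocol and SAP*

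**What the plan says.** Table 7.4 defines Grade 3 hypertension as "Systolic BP ≥ 160 mmHg or diastolic BP ≥ 100 mmHg", or as a need for more than one drug or for more intensive therapy than before. Either pressure is enough.

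The Grade 3 dosing instruction is "Hold regorafenib until diastolic BP ≤ 90 mm Hg, and if symptomatic, until symptoms resolve". Restart is at the same dose level. The treatment aim in that row is a diastolic pressure of at most 90, with no systolic figure. A later bullet adds: "If BP is not controlled with the addition of new or more intensive therapy, reduce by 1 dose level". A further reduction follows if Grade 3 hypertension recurs despite the first reduction and treatment. Footnote a takes a subject off protocol therapy after a delay of more than 4 weeks.

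In the Grade 2 row the aim is again diastolic only. Drug continues unless there are symptoms, in which case the rule is "If symptomatic, hold regorafenib until symptoms resolve AND diastolic BP ≤ 90 mm Hg".

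The text of Section 7.2.4 says that management of hypertension "will be performed according to local standards and to the usual practice of the Investigator", and it calls the table's dose reductions suggested. It does use systolic pressure for one purpose: a subject must contact study staff if, on a measurement away from the site, "the blood pressure is > 140 mm Hg systolic or > 90 mm Hg diastolic".

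**The concern.** A hold rule needs an end condition that is false when the hold begins; otherwise it holds nothing. Here systolic pressure can start the hold but plays no part in ending it. For a subject whose raised pressure is purely systolic and who has no symptoms, the rule asks for an interruption and permits restart in the same reading.

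Section 7.2.4 names hypertension as a known adverse event of regorafenib. If the row is followed as written, drug may resume at an unchanged dose with systolic pressure still in the Grade 3 range, and investigators have no common systolic limit for restart. This is a matter of subject safety and of consistent dosing across sites. It does not bear on the efficacy test.

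**Working it through.** No published figure needs reproducing. The check is whether trigger and release can both be true at the start of the hold.

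**Inputs (Table 7.4, Grade 3 row)**

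- Trigger T: SBP ≥ 160, or DBP ≥ 100, or more intensive therapy needed.
- Release R: DBP ≤ 90, and either no symptoms or symptoms resolved.
- Aim A: DBP ≤ 90.

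**Worked example: 175/85, no symptoms** (values chosen for illustration)

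- T: 175 ≥ 160, true.
- R: 85 ≤ 90 and no symptoms, true.
- A: 85 ≤ 90, true.
- Minimum hold: 0 days, so footnote a's 4-week clock has nothing to count unless the investigator chooses to wait.
- Excess over the Grade 3 systolic limit at restart: 175 − 160 = 15 mm Hg.
- Excess over the systolic limit for contacting staff in 7.2.4: 175 − 140 = 35 mm Hg.

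**All Grade 3 cases triggered by a pressure reading**

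| Situation at hold start | Release already met? | Systolic needed for release? |
|---|---|---|
| SBP ≥ 160, DBP ≤ 90, no symptoms | Yes | No |
| SBP ≥ 160, DBP ≤ 90, symptoms | No; waits for symptoms | No |
| SBP ≥ 160, DBP > 90 | No; waits for DBP ≤ 90 | No |
| SBP < 160, DBP ≥ 100 | No; waits for DBP ≤ 90 | No |

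The hold is empty only in the first line. In the second and third it has content, but it can still end with systolic pressure at 160 or more. The symptomatic Grade 2 hold behaves like the second line: it is not empty, but it has no systolic requirement. Asymptomatic Grade 2 is never held, so only its diastolic-only aim is at issue.

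**Does another rule fill the gap?** Table 7.1, the general toxicity table, does not apply. Section 7.2.2 introduces it with "The following tables outline dose adjustments for toxicities related to study drug except hand-foot skin reaction, hypertension and liver function test abnormalities". The Grade 3 rules in Section 7.2 compare as follows:

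| Table | Grade 3 hold ends when | Dose on restart |
|---|---|---|
| 7.1 general | Grade 2 or lower | One level lower |
| 7.3 hand-foot skin reaction | Grade 0–1, at least 7 days | One level lower |
| 7.5 liver tests | Grade 1 or lower (Grade 2 if that was baseline) | One level lower |
| 7.4 hypertension | DBP ≤ 90, any symptoms resolved | Same level |

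Three of the four require the grade to fall; Table 7.4 does not.

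**Time to the next scheduled check (Section 4.3.4).** Blood pressure is measured weekly for 6 weeks and every two weeks after that. The next scheduled reading may thus be up to 7 or 14 days away, unless one is taken sooner as clinically indicated.

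**Reach.** The documents give no share of subjects with isolated systolic elevation. Section 2.2.2 reports hypertension of Grade 3 or higher at 7% in the colorectal trial and 48.5% in the GIST trial, both at 160 mg. If either rate applied here, which is an assumption across tumour types and starting doses, 0.07 × 32 ≈ 2 to 0.485 × 32 ≈ 16 subjects would reach the Grade 3 row. Those with diastolic pressure of at most 90 are an unknown part of that number.

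**The case against.** The strongest reply is that the row is not meant to be read mechanically. Section 7.2.4 defers to local practice and calls the reductions suggested. The 175/85 subject must still have antihypertensives started, increased or added. Nothing compels an immediate restart, and footnote a applies if the investigator keeps holding. Section 3.4 requires withdrawal if continuing would be harmful. All of this stands as mitigation. But none of it supplies a systolic restart value, and Section 14.1 requires strict adherence to the protocol. Table 7.3 expressly allows more conservative management in its footnote a; Table 7.4 has no such footnote.

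Second, two bullets do respond to systolic pressure. The reduction for uncontrolled pressure speaks of blood pressure generally, and Section 3.2.b gives numbers for uncontrolled hypertension (systolic above 140 or diastolic above 90 on repeated measurement). The recurrence bullet relies on the Grade 3 definition, which includes systolic pressure. This is fair, but both bullets govern the dose, not the end of the hold, and 3.2.b is an eligibility criterion that Table 7.4 does not adopt.

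Third, comparison with the other tables has limits. A subject well controlled on two drugs can remain Grade 3 by definition, so a release based on grade would block restart without good reason. This stands: a pressure-based release is the right form here. The fault is that it uses one of the two pressures.

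Finally, the subset is narrow and uncounted, and uncontrolled hypertension is excluded at entry. That limits the expected number of subjects but does not make the rule work for them.

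**Conclusion.** The concern holds. For every asymptomatic subject with systolic pressure of at least 160 and diastolic of at most 90, the Grade 3 hold in Table 7.4 is released as it starts, and restart at the same dose level is permitted with systolic pressure still in the Grade 3 range. The conclusion follows from the table's wording and needs no assumption about event rates; the 15 and 35 mm Hg figures belong to the example only. How many of the 32 subjects would be affected cannot be stated from the documents. Treatment, dose-reduction steps and clinical judgement lower the practical risk. Sample size, significance level, power and the 8-of-32 decision rule are not affected. It is a small safety-rule error that should be corrected.

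**What to change.** Add a systolic condition to Table 7.4 in three places:

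1. the treatment aim in the Grade 2 and Grade 3 rows;
2. the end-of-hold condition in the Grade 3 row;
3. the end-of-hold condition for symptomatic Grade 2.

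A workable Grade 3 release would be: systolic ≤140 mm Hg and diastolic ≤90 mm Hg, with any symptoms resolved. This uses the pair of limits already in Sections 7.2.4 and 3.2.b. The final systolic value is the sponsor's clinical choice.

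The cost is wording in two table rows, and the readings are already taken at visits. The downside is that some subjects will be held longer, and a few could pass the 4-week limit in footnote a and go off protocol therapy. The sponsor should weigh that when choosing the value.

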### 7.2.5. Dose Adjustments for Liver Function Test Abnormalities

For subjects with observed worsening of serum liver tests considered related to regorafenib (i.e. where no alternative cause is evident, such as post-hepatic cholestasis or disease progression), the dose modification and monitoring advice in Table 7.5 should be followed.

Regorafenib is a UGT1A1 inhibitor. Mild, indirect (unconjugated) hyperbilirubinemia may occur in subjects with Gilbert's syndrome.

**Table 7.5: Dose modifications/interruption for ALT and/or AST and/or Total Bilirubin increases related to study drug**

Observed elevations	1 st Occurrence	Restart	Re-occurrence
baseline G0 $\rightarrow$ G1 or baseline G1 $\rightarrow$ G2	Treat on time and check AST, ALT and bilirubin 2x/week for 2 weeks followed by weekly assessments for at least 4 weeks.		Treat on time and check AST, ALT and bilirubin 2x/week for 2 weeks followed by weekly assessments for at least 4 weeks.
baseline G0 $\rightarrow$ G2	Delay until $\leq$ G1 and check AST, ALT, bilirubin 2x/week.	Reduce 1 dose level and check AST, ALT, bilirubin 2x/week for 2 weeks followed by weekly assessments for at least 4 weeks. a	Discontinue

Baseline any grade → G3	
Delay until <math>\leq</math> G1 if baseline was G0 or G1 OR until G2 if baseline was G2.
 
Check AST, ALT, bilirubin 2x/week.
 
If ALT or AST <math>> 8 \times</math> ULN with a concomitant rise in bilirubin (of any degree) compared to previous bilirubin values, consider permanent discontinuation at the first occurrence.
	
Reduce 1 dose level and check AST, ALT, bilirubin 2x/week for 2 weeks followed by weekly assessments for at least 4 weeks.a
	Discontinue
Before regorafenib initiation and during the first 2 cycles of treatment, ALT, AST and bilirubin must be monitored at least every 2 weeks.			
a: If toxicity returns to $\leq$ Grade 1 after dose reduction, dose re-escalation is permitted at the discretion of the treating Investigator per Section 6.1.1.2 for first occurrence only.			

### 7.2.6. Prevention and Management of Diarrhea

Diarrhea can be a common side effect of regorafenib. The preventive/management strategies for diarrhea should be consistent with local standards (e.g., anti-diarrheals and optimized hydration status) and at the Investigator's discretion.

Anti-diarrhea medications may be introduced if symptoms occur. Previous trials have shown that the diarrhea could be managed with loperamide. The recommended dose of loperamide is 4 mg at first onset, followed by 2 mg every 2 to 4 hours until diarrhea-free for 12 hours.

### 7.3. Adverse Event Grading

CTCAE term (AE description) and grade: The descriptions and grading scales found in the revised NCI Common Terminology Criteria for Adverse Events (CTCAE) version 4.0 will be utilized for AE reporting. All Levine Cancer Institute staff will have access to a copy of the CTCAE version 4.0.

Grade refers to the severity (intensity) of the AE:

**CTCAEv4 Grade 1:** mild; asymptomatic or mild symptoms; clinical or diagnostic observations only; intervention is not indicated.

**CTCAEv4 Grade 2:** moderate; minimal, local, or noninvasive intervention is indicated; limiting to age-appropriate instrumental activities of daily living (ADL; instrumental ADL refers to preparing meals, shopping for groceries or clothes, using the telephone, managing money, etc.).

**CTCAEv4 Grade 3:** severe or medically significant but not immediately life threatening; hospitalization or prolongation of hospitalization is indicated; disabling; limiting to self-care ADL (self-care ADL refers to bathing, dressing and undressing, feeding self, using the toilet, taking medications, and not bedridden).

**CTCAEv4 Grade 4:** life-threatening consequences; urgent intervention is indicated.

**CTCAEv4 Grade 5:** death due to an AE

#### 7.4. Adverse Event Attribution

The assessment is based on the question whether there was a “reasonable causal relationship” to the study treatment in question. AEs are considered to be “not related” or “related” to the study drug according to the following definitions:

**Not Related:** Evidence exists that the AE has an etiology other than the study drug (eg, pre-existing condition, underlying disease, intercurrent illness, or concomitant medication). This includes events that are considered remotely or unlikely related to study drug.

**Related:** A temporal relationship exists between the event onset and administration of the study drug. It cannot be readily explained by the subject’s clinical state, intercurrent illness, or concomitant therapies. In the case of cessation or reduction of the dose, the event abates or resolves and reappears upon rechallenge. It should be emphasized that ineffective study drug treatment should not be considered as causally related in the context of AE reporting. This includes events that are considered possibly, probably, or definitely related to study drug.

***Final attribution should be stated as follows (choose only one):***

Definite – The AE is *clearly related* to the study treatment.

Probable – The AE is *likely related* to the study treatment.

Possible – The AE *may be related* to the study treatment.

Unlikely – The AE *is doubtfully related* to the study treatment.

Unrelated – The AE *is clearly NOT related* to the study treatment.

## 7.5. Adverse Event Action and Outcome

Any action on study treatment to resolve the AE is to be documented using the categories listed below:

- Drug withdrawn
- Drug interrupted
- Dose reduced
- Dose not changed
- Dose increased
- Not applicable
- Unknown

The outcome of the AE is to be documented as follows:

- Recovered/resolved
- Recovering/resolving
- Recovered/resolved with sequelae
- Not recovered/not resolved
- Fatal
- Unknown

## 8. DATA AND SAFETY MONITORING PLAN

### 8.1. Safety Monitoring

This trial will be monitored according to the processes in effect for all Levine Cancer Institute Investigator- Initiated Trials and will abide by standard operating procedures set forth by both the Carolinas Medical Center Office of Clinical and Translational Research and the Levine Cancer Institute Clinical Trials Department. It is the responsibility of the Sponsor-Investigator to monitor the safety data for this study. On at least a monthly basis, the Sponsor-Investigator, Study Statistician and Protocol Coordinator will meet to monitor subject consents, enrollment and retention, safety data for all subjects [including adverse events (AE's) for all grades and attributions, serious adverse events (SAE's)], study drug administration, and validity/integrity of the data. SAEs will be reported to the IRB per their requirements. Major protocol deviations that result in a threat to subject safety or the integrity of the study will be reported to the IRB per their requirements. Following each meeting, a status will be

generated and kept on file in the LCI Clinical Trials Office with study records. The Sponsor-Investigator will submit reports to the LCI Data and Safety Monitoring Committee according to the overarching LCI Data and Safety Monitoring Plan.

## **8.2. Data Quality Assurance**

This study will be organized, performed, and reported in compliance with the study protocol, standard operating procedures (SOPs) of Levine Cancer Institute and Carolinas Medical Center Office of Clinical and Translational Research, the FDA, and other applicable regulations and guidelines (e.g. GCP).

Data will be collected on electronic CRFs in the CTMS.

Subjects will be monitored by Levine Cancer Institute Research Monitors routinely for data quality. This monitoring will be done by comparing source documentation to the CRFs. Any variation between the two data sets will be discussed with the Protocol Coordinator or Sponsor-Investigator.

The study database will be reviewed and checked for omissions, apparent errors, and values requiring further clarification using computerized and manual procedures. Data queries requiring clarification will be generated and addressed by the appropriate study team member and/or Sponsor-Investigator. Only authorized personnel will make corrections to the study database and all corrections will be documented in an electronic audit trail.

